### 2.3. Screen failures

Volunteers that do not enroll on HVO-vCS-003 will be recorded as screen failures and may be eligible to participate in other studies.

- Are you a smoker or ex-smoker? If so, how many cigarettes per day and how long for?
- Are you currently suffering from any illness or health-related condition? (coughs, colds, stomach problems, chest complaints, dizziness, eczema, headaches etc.)
- Have you ever been diagnosed with anxiety or depression?
- Are you taking medicines prescribed by a doctor or bought from chemist/pharmacy (includes contraception, vitamins, supplements)?
- Are you or your partner trying to get pregnant?
- Do you have any viral blood conditions (e.g. HIV, Hepatitis A, B or C)?
- Are you employed or related to anybody at hVIVO?
- Do you have asthma?
- Have you had Asthma in childhood?
- Do you have COPD as diagnosed by a doctor?
- Complete a COVID-19 symptom assessment

If inclusion/exclusion criteria are provisionally met based on answers to these questions, an appointment for a first screening visit will be scheduled and a confirmation email and a screening Participant Information Sheet (PIS)/Informed Consent Form (ICF) will be sent to volunteers.

Screening appointments will be conducted at hVIVO. First, the screening process will be discussed with the participant by the study doctor or nurse. When the subject has had enough time to consider their participation in screening, ask any questions they may have, and only when they have agreed to take part will they be asked to read, sign and date a consent form in the presence of the study doctor or nurse who will also sign the consent form. Written consent for screening will be obtained prior to any history-taking, examination or tests are carried out. A copy will be kept in the research file, a copy given to the patient and a copy put into their medical notes.

Following informed consent, the following assessments will be completed.

- Confirmation of name, age, gender, and contact details
- Full medical history including questions about past and present health including clinically significant family history
- Optional - Quality of life questionnaires including the GAD-7 Anxiety Test questionnaire and PHQ-9 Depression Test questionnaire.
- Questions about current weekly alcohol and/or smoking consumption and an alcohol breath test will be performed.
- Check of any previous participation in clinical trials via The Over-Volunteering Prevention System (TOPS).
- Examination for signs of illness or disease (a medical examination).
- Height and weight
- Pulse rate, blood pressure, temperature and breathing rate checked (Vital Signs).
- Electrocardiogram (ECG)
- Urine samples for:

- Evidence of infection or kidney/urinary tract conditions
- Test for pregnancy
- For drugs of abuse & cotinine
- Provide an airway sample (i.e. nasal swab as a tolerance test for the respiratory screen for pathogens and/or immune status). It will be optional to conduct a BioFire test at the discretion of the PI.
- Safety blood tests, including full blood count, renal and liver function tests.
- Testing for SARS-CoV-2 virus (COVID-19) antibodies
- Samples for Hepatitis A, B and C and/or HIV (the virus that causes AIDS)
- Lung function tests.

Inclusion and exclusion criteria will be assessed based on evidence available at the time of screening, any non-applicable aspects of the criteria will be checked upon admission.

The volunteer's medical history will be requested from their GP and reviewed to assess suitability. Subjects may be invited for repeat assessment where / if required at the PI's discretion. For participants contacted via the hVIVO volunteer database, GP medical histories that have been previously received by hVIVO may be used for screening purposes if they were obtained within the screening window of the study (i.e. within 90 days to -3 days prior to date of virus inoculation).

As soon as the SARS-CoV-2 human challenge characterization study is approved, potential participants who have passed screening up to that point will be given or sent the study specific participant information sheet (PIS) detailing the full study and experimental procedures. This will be done in advance of the first study specific visit to give participants enough time to read the PIS, discuss the study with family and friends, as well as being able to call the hVIVO medical team to ask any questions they may have. A follow-up appointment (to be conducted remotely due to the COVID-19 pandemic) will be arranged to go through the details of the study with a study team member and to answer any questions, if this was not already done at the screening visit. Additional calls may be arranged as needed. Participants will be advised that they will be required to self-isolate (stay at home) for up to 7 days immediately prior to admission to the Quarantine Unit. They will also be asked to take a nasal pharyngeal swab (NPS) 72 hours prior to admission to be returned to hVIVO for PCR testing. The samples from this test will be collected by a courier and delivered to the hVIVO laboratory to be analysed.

When the subject has had enough time to consider their participation in this study, ask questions and if they are still willing to take part in the study, they will be invited to be admitted to the quarantine unit (Day -2). Before any study specific procedures are attempted, the study physician will again discuss the study and study procedures with the potential participant and answer any questions. After that, participants will be asked to read, sign and date the full study ICF in the presence of the study doctor or nurse, who will also sign the consent form. A copy of the consent will be given to the participant and another copy will be filed in their medical notes.

## 4. Supporting Documentation and Operational Considerations

### 4.1. Appendix 1: Regulatory, Ethical, and Study Oversight Considerations

#### 4.1.1. Regulatory and Ethical Considerations

This study will be conducted in accordance with the protocol and with the following:

- Consensus ethical principles derived from international guidelines including the Declaration of Helsinki and Council for International Organizations of Medical Sciences (CIOMS) International Ethical Guidelines
- Applicable ICH Good Clinical Practice (GCP) Guidelines
- Applicable laws and regulations

#### 4.1.2. Ethics approval

The Study Coordination Centre has obtained approval from the Specialist Adhoc Research Ethics Committee (REC). The study will be conducted in accordance with the recommendations for physicians involved in research on human subjects adopted by the 18th World Medical Assembly, Helsinki 1964 and later revisions.

#### 4.1.3. Consent

The Investigator will obtain a signed screening ICF from each participant before any screening or study specific procedures are performed as described in section 3.

Potential participants will be sent a copy of the Screening ICF when their Screening Visit is arranged and at least one day prior to the visit, and will be encouraged to read it prior to their appointment. Upon arrival at the Screening Visit the Screening ICF is discussed, and they will be given the opportunity to ask any questions, and may take the information sheet away to consider their participation. Participants will be informed that a further discussion with the full study PIS/ICF will be scheduled at a later point (if necessary) and that they will be free to withdraw at any point before or after that.

All participants will be required to have a good understanding of English and the Investigator will be responsible for ensuring that the subject understands the information contained in the ICFs. Once they have confirmed that the subject has understood the study, including the benefits and risks of participation, the subject and the Investigator can sign and date the ICF.

The ICF must be signed and dated by the subject and countersigned by the Investigator (whoever conducted the consent discussion). A copy of the ICF will be given to the subject, and the original will be held in the full study TMF. The consent process will be documented in line with hVIVO SOPs, which require that documented and signed evidence must be available to confirm staff obtaining consent are trained and passed as competent, prior to independently obtaining consent. The Investigator will document the consent process in the subject notes and progress notes as

applicable. This documentation will include details of capacity assessment, discussion with subject, and when/how consent has been obtained.

Participants who were consented prior to implementation of Substantial Amendment 2 will require re-consent to incorporate the up to 7 day stay at home isolation period and PCR test. This process will be done remotely to avoid unnecessary travel by the participants. The process will be as follows:

- 1) The participant will be emailed (if they have a printer) or posted (if they do not have a printer or indicate this as a preference) a copy of the PIS/ICF.
- 2) A zoom call will be arranged between the participant and the research physician.
- 3) The new procedures will be explained to the participant and the option to ask any questions will be presented.
- 4) The participant and the research physician will each sign a copy of the PIS/ICF. The research team will then arrange for a courier to collect the partially signed PIS/ICF from the participant's home and it will be collated with the partially signed PIS/ICF on site. Once the documents are combined the consent will be considered valid.
- 5) The participant will be posted a copy of the consent via tracked delivery

Participants will be assured that they can withdraw from the study at any time and for any reason without prejudice to their future medical care, and that they will be informed in a timely manner if new information becomes available that may affect their willingness to continue their participation in the study. This information will be included within the ICF.

The ICF will contain a separate section that addresses the use of samples for future research. The investigator or authorised designee will explain to each participant the objectives of the exploratory research. Participants will be told that they are free to refuse to participate and may withdraw their consent at any time and for any reason.

#### **4.1.4. Confidentiality**

The Chief Investigator will preserve the confidentiality of participants taking part in the study and is registered under the Data Protection Act.

#### **4.1.5. Indemnity**

Imperial College London holds negligent harm and non-negligent harm insurance policies which apply to this study. hVIVO holds negligent harm insurance policies which apply to this study.

#### **4.1.6. Sponsor**

Imperial College London will act as the Sponsor for this study. Delegated responsibilities will be assigned to hVIVO Services Ltd.

#### 4.1.7. Funding

This study is funded by the UK Vaccines Taskforce and Department of Business, Energy and Industrial Strategy. They are acting as sole funders and this agreement is in place. The investigators will not receive any additional payment above their normal salaries. Participants will be given a donation of up to £70 to compensate for the time and inconvenience of attending the screening visit. Additional visits will be compensated with £20 per visit.

#### 4.1.8. Audits

The study may be subject to audit by Imperial College London under their remit as sponsor and other regulatory bodies to ensure adherence to GCP and the UK Policy Framework for Health and Social Care Research.

#### 4.1.9. Sample and data storage and usage

Samples of tissue, cells and fluids will be stored according to Imperial College London and hVIVO SOPs as appropriate. Samples will be pseudoanonymised with participant identification numbers only and the anonymisation key kept in a separate locked location accessible only to the hVIVO clinical study team. Samples may be used for further assays or in other ethically approved studies. Samples and data may be shared with UK and international collaborators in studies that have been approved by local ethics committees and subject to a valid Materials Transfer Agreement. Data and samples sent outside the UK will be labelled with the identification number only and no patient identifiable data transferred. Screening data is recorded on paper case books. Data is QC'd and only data for enrolled subjects is transcribed to the study data base, as per the hVIVO Data Monument Plan. Data and all appropriate documentation will be stored for a maximum of 25 years after the completion of the study, including the follow-up period according to Imperial College London policy.

At the end of the study any remaining samples will be either destroyed, transferred to the sponsor or subject to consent, transfer to and maintained under hVIVO's HTA licenses.

#### 4.1.10. Data Protection

Participants will be assigned a unique identifier by hVIVO. Any participant records or datasets that are transferred to the Sponsor will contain the identifier only; participant names or any information which would make the participant identifiable will not be transferred.

The participant must be informed that his/her personal study-related data will be used by the Sponsor in accordance with local data protection law and EU GDPR. The level of disclosure including the participant's rights under the applicable data protection laws must also be explained to the participant in the ICF.

The participant must be informed that his/her medical records may be examined by third parties such as Clinical Quality Assurance auditors or other authorized personnel appointed by the Sponsor, by appropriate REC members, and by inspectors from regulatory authorities.

## 4.2. Appendix 2: Adverse events

### 4.2.1. Definitions

**Adverse Event (AE):** any untoward medical occurrence in a patient or clinical study subject.

**Serious Adverse Event (SAE):** any untoward and unexpected medical occurrence or effect that:

- **Results in death**
- **Is life-threatening** – refers to an event in which the subject was at risk of death at the time of the event; it does not refer to an event which hypothetically might have caused death if it were more severe
- **Requires hospitalisation**
- **Results in persistent or significant disability or incapacity**
- **Is a congenital anomaly or birth defect**

Medical judgement should be exercised in deciding whether an AE is serious in other situations. Important AEs that are not immediately life-threatening or do not result in death or hospitalisation but may jeopardise the subject or may require intervention to prevent one of the other outcomes listed in the definition above, should also be considered serious.

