### 4.2.2. Risks and expected adverse events

#### 4.2.2.1. Risk Determination

All screening procedures involve no more than minimal risk to participants. Similar procedures have been used for many years without severe adverse effects. These include blood sampling and ECG. Participants will be counselled about the following:

Blood draws: risks include discomfort as the needle goes through the skin and/or bruising. Infection, excess bleeding, clotting, or fainting are also possible, although unlikely.

ECG: risks include skin irritation due to ECG electrodes.

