##### 5.3.2 Serious AEs

An SAE form should be completed and emailed to the Chief Investigator within 24 hours.

All SAEs should be reported to the Research Ethics Committee where in the opinion of the Chief Investigator, the event was:

- 'related', i.e. resulted from the administration of any of the research procedures; and
- 'unexpected', i.e. an event that is not listed in the protocol as an expected occurrence

Reports of related and unexpected SAEs should be submitted within 15 days of the Chief Investigator becoming aware of the event, using the NRES SAE form for non-IMP studies. The Chief Investigator must also notify the Sponsor of all SAEs.

Local investigators should report any SAEs as required by their Local Research Ethics Committee, Sponsor and/or Research & Development Office.

**Contact details for reporting SAEs**[[contact]](mailto:[contact])**CI email (and contact details below)****Email: [[contact]](mailto:[contact]) for the attention [name]****Please send SAE forms to: Department of Infectious Disease, Imperial College London, [name]****[contact] (Mon to Fri 09.00 – 17.00)**

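### The SAE definition includes 'unexpected', contradicting the later expectedness test, so a listed complication that hospitalises a volunteer can miss the 24-hour form and sponsor notification

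*Protocol*

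**What the plan says.** Section 4.2.1 (Definitions) defines an adverse event (AE) as "any untoward medical occurrence in a patient or clinical study subject", with no reference to expectedness. It then defines an SAE as "any untoward and unexpected medical occurrence or effect that" meets one of five outcomes, one of which is "Requires hospitalisation". A closing paragraph adds: "Medical judgement should be exercised in deciding whether an AE is serious in other situations". It extends seriousness to certain important AEs that jeopardise the subject or may need intervention.

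Section 4.2.2 is headed as covering risks and expected adverse events. Under it, section 4.2.2.1 says of blood draws: "Infection, excess bleeding, clotting, or fainting are also possible, although unlikely". It also mentions discomfort and bruising, and skin irritation from ECG electrodes.

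Section 4.2.3 asks for all AEs to be reported. Within it, the subsection numbered 5.3.1 asks for non-serious AEs to be recorded whether expected or not, and gives no deadline. The subsection numbered 5.3.2 says "An SAE form should be completed and emailed to the Chief Investigator within 24 hours" and requires the Chief Investigator to tell the sponsor of every SAE. It then limits the 15-day REC report to SAEs that are both related and unexpected, where unexpected means "an event that is not listed in the protocol as an expected occurrence".

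**The concern.** Seriousness is a matter of outcome; expectedness is a matter of whether the protocol already lists the event. Section 5.3.2 keeps the two apart and section 4.2.1 merges them. The lead-in to the SAE definition governs all five outcomes, so the word 'unexpected' conditions each of them, including hospitalisation.

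At stake is the reporting route for a healthy volunteer harmed by a screening procedure. The complications that the protocol names in advance are the ones the definition shuts out. If one of them puts a volunteer in hospital, the wording does not require the 24-hour form or the sponsor notification.

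**Working it through.** No arithmetic applies and the plan gives no figure to reproduce. The check is to read the sections against one another.

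**Step 1: what 'unexpected' means.** Section 4.2.1 does not define it. The only definition in the document is in section 5.3.2: "an event that is not listed in the protocol as an expected occurrence". It turns on listing and does not mention severity. I assume that the word has the same meaning in both places.

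**Step 2: which events are listed.** Section 4.2.2.1, under the heading on expected adverse events, names infection, excess bleeding, clotting and fainting after blood draws. The other listed effects (discomfort, bruising, skin irritation) matter little here.

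**Step 3: a worked case.** A volunteer is hospitalised with an infection after a blood draw.

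| Test | Section | Result |
|---|---|---|
| Untoward medical occurrence? | 4.2.1 | Yes, so it is an AE |
| One of the five outcomes? | 4.2.1 | Yes, hospitalisation |
| Unexpected? | 4.2.1, with the meaning in 5.3.2 | No, it is listed in 4.2.2.1 |
| SAE under the main definition? | 4.2.1 | No |
| 24-hour form and sponsor notification required? | 5.3.2 | No, both attach to SAEs only |
| Reported or recorded as an AE? | 4.2.3 and 5.3.1 | Yes, with no deadline |

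**Step 4: the contradiction.** Write S for an event that meets one of the five outcomes, U for unexpected and R for related.

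- As written, SAE = S and U. The REC set is (S and U) and R and U, which reduces to S and U and R. The second U does nothing.
- With expectedness removed from the definition, SAE = S. The REC set is S and R and U, the same as before.
- The only difference is S without U: expected events with a serious outcome. They gain the 24-hour form and the sponsor notification.

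Events that become serious through the clause on other important AEs carry no expectedness condition under either wording, so the change does not affect them.

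**Step 5: how good the fallback is.** The untimed AE route is weaker than the SAE route. Section 5.3.1 still contains a template instruction to specify whether only some non-serious AEs will be recorded. Section 4.1.9 says that screening data are kept on paper and that only enrolled subjects' data enter the study database. An event in a volunteer who is hospitalised during screening and never enrols could therefore stay in a paper case book.

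**The case against.** The strongest reply is that section 4.2.1 has its own safety net. The paragraph on medical judgement speaks of AEs, which are defined without an expectedness test. A listed bleed, clot or infection that needs intervention to prevent a worse outcome is therefore serious under the protocol. This stands for events short of hospitalisation. For hospitalised events it is only arguable: the paragraph opens by addressing other situations, and its conditions are joined by 'or' in a way that can be read to include or exclude them. An investigator may use it to call such an event serious, but nothing clearly requires that.

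It can also be said that a complication bad enough for hospital admission is not the minimal-risk occurrence listed in section 4.2.2.1, and so counts as unexpected. That reading is open, but section 5.3.2 says nothing on severity, so it rests on the reader and not on the text.

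Four stronger conclusions that a reader might draw are not supported:

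- That listed events can never be SAEs. The clause on other important AEs can make some of them serious.
- That expected serious events go wholly uncaptured. Sections 4.2.3 and 5.3.1 still require them to be reported or recorded as AEs. What is lost is the SAE classification and the two duties attached to it.
- That the REC test becomes empty. Its relatedness limb still works; only the expectedness limb is redundant, and only for events qualifying through the five outcomes.
- That SAE counts or rates are biased. This screening protocol states no SAE rate, safety endpoint or safety analysis, so there is no estimate to bias.

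**Conclusion.** The point holds as an internal contradiction with a specific reporting gap. Sections 4.2.1 and 5.3.2 give expectedness two incompatible roles. Followed literally, the first leaves a listed complication that leads to hospitalisation outside the 24-hour form and the sponsor notification. Because section 5.3.2 tests expectedness again, this looks like a drafting slip and not a deliberate choice.

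The practical size is small. Section 4.2.2.1 describes the screening procedures as minimal risk and these complications as unlikely, and the document gives no event rate from which a number could be derived. The conclusion rests on two assumptions: that 'unexpected' has the section 5.3.2 meaning throughout, and that the events named in section 4.2.2.1 are the protocol's listed expected occurrences, as the heading above them indicates.

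**What to change.** Delete the words 'and unexpected' from the lead-in to the SAE definition in section 4.2.1, so that seriousness depends on outcome alone. Leave section 5.3.2 as it is, with expectedness serving only, alongside relatedness, as a criterion for the 15-day REC report.

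The cost is two words in an amendment and at most a few more SAE forms and sponsor notifications. REC reporting is unchanged, as step 4 of the working shows.
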